## 6.5 Other efficacy endpoints

### 6.5.1 Variables

- Changes from baseline to Week 2 of DB treatment in mean trough SiSBP and SiDBP measured by AOBPM.
- Changes from baseline to Week 4 in daytime and nighttime mean SBP and DBP measured by 24 h ABPM:
  - Daytime is defined as between 09:00 and 21:00.
  - Nighttime is defined as between 01:00 and 06:00 [[O'Brien 2013](#)].
- Changes from DB-WD baseline (Week 36) to Week 38, Week 44 and Week 48 of DB-WD treatment in mean trough SiSBP and SiDBP measured by AOBPM.
- Changes from DB-WD baseline (Week 36) to Week 40 in daytime and nighttime mean SBP and DBP measured by 24 h ABPM.
- Ratios to baseline for all assessed time points in the DB and SB aprocitentan parts and to DB-WD baseline (Week 36) for all assessed time points in the DB-WD part in UACR.
- Discontinuation of randomized study treatment due to lack of efficacy (as collected on the **Study Treatment Log**) by study part (DB, SB aprocitentan and DB-WD).
- Initiation of antihypertensive rescue medication (as indicated on the **Previous/Concomitant Medication** eCRF) in the SB aprocitentan part or DB-WD part. (Rescue medication is not allowed in the DB part).
- Observed values of home SBP/DBP by visit collected due to the COVID-19 pandemic in the DB, SB aprocitentan, and DB-WD parts.

The following endpoints related to BP control and response were added as compared to the protocol [refer to [Section 11](#)]:

- Binary control variables will be created at each visit for SiSBP and SiDBP measured by AOBPM:
  - SBP Control = ‘Yes’ if patient achieved a mean trough SiSBP of < 135 mmHg or < 140 mmHg at the visit. SBP Control= ‘No’ otherwise.
  - DBP Control = ‘Yes’ if patient achieved a mean trough SiDBP of < 85 mmHg or < 90 mmHg at the visit. DBP Control= ‘No’ otherwise.
  - SBP/DBP control = ‘Yes’ if patient achieved a mean trough SiSBP of < 135 mmHg and SiDBP of < 85 mmHg or SiSBP of < 140 and SiDBP of < 90 mmHg at the visit. SBP/DBP control = ‘No’ otherwise.

- Binary response variable will be created at each visit in the DB and SB parts of the study for SiSBP and SiDBP measured by AOBPM:
  - SBP Response = ‘Yes’ if patient achieved a reduction in SiSBP from baseline of  $\geq 10$  mmHg or  $\geq 15$  mmHg in the DB and SB aprocitentan parts. SBP Response = ‘No’ otherwise.
  - DBP Response = ‘Yes’ if patient achieved a reduction in SiDBP from baseline of  $\geq 5$  mmHg or  $\geq 10$  mmHg in the DB and SB aprocitentan parts. DBP Response = ‘No’ otherwise.
  - SBP/DBP Response = ‘Yes’ if patient achieved a reduction in SiSBP from baseline of  $\geq 10$  mmHg and SiDBP of  $\geq 5$  mmHg or achieved a reduction in SiSBP from baseline  $\geq 15$  mmHg and SiDBP of  $\geq 10$  mmHg at the visit. SBP/DBP response = ‘No’ otherwise.
- A binary response variable will also be created for each visit in the DB-WD part (in which a blood pressure increase may occur)
  - SBP Withdrawal Response = ‘Yes’ if patient achieved an increase in SiSBP from DB-WD baseline of  $\geq 5$  mmHg or  $\geq 10$  mmHg in the DB-WD part. SBP Withdrawal Response = ‘No’ otherwise.
  - DBP Withdrawal Response = ‘Yes’ if patient achieved an increase in SiDBP from DB-WD baseline of  $\geq 3$  mmHg or  $\geq 6$  mmHg in the DB-WD part. DBP Withdrawal Response = ‘No’ otherwise.
  - SBP/DBP Withdrawal Response = ‘Yes’ if patient achieved an increase in SiSBP from DB-WD baseline of  $\geq 5$  mmHg and SiDBP of  $\geq 3$  mmHg or an increase in SiSBP from DB-WD baseline of  $\geq 10$  mmHg and SiDBP of  $\geq 6$  mmHg. SBP/DBP Withdrawal response = ‘No’ otherwise.

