- *The number (%) of subjects who discontinued study treatment due to lack of efficacy will be tabulated by study part (DB, SB aprocitentan and DB-WD) and treatment group (within study part) in the FAS (2×) and mFAS, respectively. If there are at least 12 subjects discontinued due to lack of efficacy, time from Randomization to treatment discontinuation due to lack of efficacy in the DB or SB aprocitentan part will be summarized by treatment group using Kaplan-Meier plots in the FAS. For subjects who did not discontinue treatment or discontinued treatment for reasons other than lack of efficacy, time to discontinuation will be censored at the last dose of DB or SB treatment (whichever comes last). Additionally, a ‘two-step’ Cox model with a factor for treatment will be fitted [see Section 8.2 for details]. Time from Re-randomization to treatment discontinuation due to lack of efficacy in the DB-WD part will be summarized similarly in the mSAF, except that the Cox model is the conventional one. For subjects who did not discontinue treatment or discontinued treatment for reasons other than lack of efficacy in the DB-WD part, time to discontinuation will be censored at the last DB-WD treatment + 30 days (or EOS date, whichever comes first).*
- *The number (%) of subjects who initiated antihypertensive rescue medication will be summarized by study part (SB and DB-WD; rescue medication is not allowed in the DB part) and treatment group (within study part).*
- *Home SBP/DBP collected due to the COVID-19 pandemic will be summarized by visit in DB, SB and DB-WD parts using descriptive statistics.*
- *The number (%) of subjects with SBP/DBP Control will be tabulated for the DB+SB and DB-WD parts at each visit by treatment group in the FAS and mFAS, respectively. Subjects with a missing value at a given visit will be excluded from the analysis at that visit. The Cochran-Mantel-Haenszel (CMH) test will be used to test for a difference in the Control proportions at Week 4 between treatment groups in DB part on the FAS and at Week 40 between treatment groups in DB-WD part (stratified by randomized*

treatment in the DB part) on the mFAS. The treatment effect will be expressed in terms of the aprocitentan to placebo OR and corresponding 95% CI. An OR > 1 will indicate a benefit of aprocitentan as compared to placebo.

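### SAP 6.5.1 joins two nested cut-offs with *or* in every BP control and response variable, so as written only the lax cut-off is ever analysed

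*SAP*

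**What the plan says.** SAP section 6.5.1 introduces the control endpoints thus: "Binary control variables will be created at each visit for SiSBP and SiDBP measured by AOBPM". It then gives one Yes condition for each:

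- SBP Control: "patient achieved a mean trough SiSBP of < 135 mmHg or < 140 mmHg at the visit".
- DBP Control: "patient achieved a mean trough SiDBP of < 85 mmHg or < 90 mmHg at the visit".
- SBP/DBP Control: "SiSBP of < 135 mmHg and SiDBP of < 85 mmHg or SiSBP of < 140 and SiDBP of < 90 mmHg".

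Each definition closes with a catch-all such as "SBP Control= ‘No’ otherwise".

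Response in the DB and SB parts has the same form. SBP Response is Yes if the "patient achieved a reduction in SiSBP from baseline of" at least 10 or at least 15 mmHg. The DBP thresholds are 5 or 10 mmHg, and a combined version pairs the two. Withdrawal Response in the DB-WD part is Yes if the "patient achieved an increase in SiSBP from DB-WD baseline of" at least 5 or at least 10 mmHg. Its DBP thresholds are 3 or 6 mmHg, again with a combined version.

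Section 6.5.2 tabulates these variables by visit and applies a CMH test with an odds ratio at Week 4 and Week 40, at two-sided 0.05 without multiplicity correction. On missing data it says: "Subjects with a missing value at a given visit will be excluded from the analysis at that visit". Section 11 calls the endpoints exploratory.

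**The concern.** A binary variable that is Yes when either of two nested conditions holds carries no information about the stricter one. The plan names two thresholds per endpoint, so both were presumably wanted. The 135 mmHg value is also used in section 6.3.6 to split subjects by DB-WD baseline SiSBP. Programmed literally, the SAP yields no < 135/85 control rate and no result for the larger response or withdrawal thresholds.

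A programmer who departs from the text to produce two versions gets no guidance. Section 6.5.2, Table 4 (which does not list these endpoints) and the code in section 8.2.5 (one response variable) do not say that there are two versions or which of them the test and odds ratio refer to. The threshold reported could then be settled after results are known.

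The closing catch-all raises a second question: does a subject with no reading count as No, or is that subject left out?

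**Working it through.** **1. Logic.** If condition A implies condition B, then (A or B) is the same as B. Applied to the nine definitions in section 6.5.1 (mmHg):

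| Variable | Strict | Lax | Rule as written equals |
|---|---|---|---|
| SBP Control | < 135 | < 140 | < 140 |
| DBP Control | < 85 | < 90 | < 90 |
| SBP/DBP Control | < 135 and < 85 | < 140 and < 90 | < 140 and < 90 |
| SBP Response (fall) | ≥ 15 | ≥ 10 | ≥ 10 |
| DBP Response (fall) | ≥ 10 | ≥ 5 | ≥ 5 |
| SBP/DBP Response | ≥ 15 and ≥ 10 | ≥ 10 and ≥ 5 | ≥ 10 and ≥ 5 |
| SBP Withdrawal Response (rise) | ≥ 10 | ≥ 5 | ≥ 5 |
| DBP Withdrawal Response (rise) | ≥ 6 | ≥ 3 | ≥ 3 |
| SBP/DBP Withdrawal Response | ≥ 10 and ≥ 6 | ≥ 5 and ≥ 3 | ≥ 5 and ≥ 3 |

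Comparing each rule as written with its lax cut-off over a grid of BP values and changes gave no mismatch.

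**2. Size.** The documents state no control or response rate, so there is no figure to reproduce. The means and SDs below are assumptions. With Φ the standard normal distribution function, P(SiSBP < c) = Φ((c − mean)/SD).

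| Assumed Week 4 mean, SD | P(< 140) | P(< 135) | Gap |
|---|---|---|---|
| 136, 13 | Φ(0.31) = 62% | Φ(−0.08) = 47% | 15 points |
| 136, 16 | Φ(0.25) = 60% | Φ(−0.06) = 48% | 12 points |
| 144, 13 | Φ(−0.31) = 38% | Φ(−0.69) = 24% | 13 points |
| 144, 16 | Φ(−0.25) = 40% | Φ(−0.56) = 29% | 11 points |

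Gaps are taken before rounding. For SBP Response with an assumed SD of change of 14 mmHg:

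- Mean change −5: P(fall ≥ 10) = 1 − Φ(5/14) = 36%; P(fall ≥ 15) = 1 − Φ(10/14) = 24%.
- Mean change −15: P(fall ≥ 10) = 1 − Φ(−5/14) = 64%; P(fall ≥ 15) = 1 − Φ(0) = 50%.

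**3. Missing values, texts side by side.** Section 6.5.2 excludes subjects without a value at the visit and extends the control analysis to response. Section 8.1 leaves missing values out of percentages. The catch-all in section 6.5.1 does not mention missing data. Two explicit statements therefore point to exclusion, and none scores a missing value as No.

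**4. What a failure rule would change at Week 40.** Section 6.3.2 expects 10% of the mFAS to lack a Week 40 AOBPM. Assume 60% (aprocitentan) and 45% (placebo) are controlled among those observed.

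- Missing excluded: (0.60/0.40)/(0.45/0.55) = 1.83.
- Missing as not controlled, 10% in each arm: (0.54/0.46)/(0.405/0.595) = 1.72.
- Missing as not controlled, 5% aprocitentan and 15% placebo: (0.57/0.43)/(0.3825/0.6175) = 2.14.

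**The case against.** The best defence is that *or* here lists alternatives to be reported separately. The SAP writes that way elsewhere: section 7.4.1 lists nested QTcF limits with *or*, and section 7.3.2 does the same for aminotransferase multiples. The control endpoints are introduced in the plural, and pairing 135 with 85 and 140 with 90 makes most sense as two sets. Separate variables may well have been intended. But section 7.4.2 states that the ECG categories are presented cumulatively, and nothing comparable is said for BP control and response. The response and withdrawal definitions are introduced in the singular. The defence explains the intention; it does not supply the rule.

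A reader might also infer that the catch-all conflicts with the exclusion rule, and that exclusion removes withdrawal-phase failures. The documents support neither inference. The catch-all is naturally read as the complement of Yes among subjects with a reading, and the explicit rule in section 6.5.2 governs. Nothing shows that subjects without a Week 40 reading are failures, or that they are more common on placebo. Stopping treatment does not by itself remove the reading. Table 2 schedules AOBPM at an EOT visit due within 7 days of the last dose, and the Week 40 efficacy window in Table 6 (WD days 21 to 41) has no end-of-treatment cap. Discontinuation for lack of efficacy and rescue initiation are summarised as endpoints of their own.

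**Conclusion.** The definitions are wrong as written. All nine variables equal their lax cut-off, and the strict versions are never produced. This rests on set logic alone and needs no assumption. The practical size (11 to 15 points for SBP control, 12 to 14 points for SBP response) depends on the assumed means and SDs and is only illustrative.

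The missing-data question reduces to wording. The odds ratios in step 4 move in either direction depending on the assumed split by arm. If more values were missing on placebo, exclusion would give a smaller odds ratio than failure scoring, so it would not favour aprocitentan. No bias claim can be built on this.

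The endpoints are exploratory. H10, H20 and H30, and the alpha assigned to them, are untouched.

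**What to change.** 1. In section 6.5.1, replace each two-threshold definition by two variables, one per cut-off: 9 × 2 = 18 binary variables.
2. In sections 6.5.2 and 8.2.5, state that each variable is tabulated and that the CMH test and odds ratio are given for each at Week 4 or Week 40, as applicable.
3. Keep the exclusion of missing values in section 6.5.2, and qualify the catch-all in section 6.5.1 so that No applies *among subjects with a value at the visit*.
4. Optional: a further check that scores missing values after discontinuation for lack of efficacy as failures. It is not needed to correct the plan, for the reasons given above. Extending it to stops for adverse events would be debatable, because for Withdrawal Response it would record a BP rise that nobody measured.

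The cost is SAP wording, extra table rows and repeated runs of the section 8.2.5 code. No data collection or alpha allocation changes.

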### 6.5.2 Analyses

All other efficacy variables will be tested at the two-sided significance level of 0.05. No correction for multiplicity will be applied.

- *Changes from baseline to Week 2 of DB treatment in mean trough SiSBP and SiDBP measured by AOBPM* will be analyzed using the mixed model described for changes from baseline to Week 4 in mean trough SiSBP and SiDBP, respectively.
- *Changes from baseline to Week 4 in daytime and nighttime mean SBP and DBP measured by ABPM* will be analyzed in the aFAS using the same ANCOVA as described for 24 h mean SBP and DBP.
- *Changes from DB-WD baseline (Week 36) to Week 38 of DB-WD treatment in mean trough SiSBP and SiDBP measured by AOBPM* will be analyzed in the mFAS using the mixed model described for changes from DB-WD baseline (Week 36) to Week 40 in mean trough SiSBP and SiDBP, respectively.

- *Changes from DB-WD baseline (Week 36) to Weeks 40 and 48 of DB-WD treatment in mean trough SiSBP/SiDBP measured by AOBPM will be analyzed in the mFAS using the same mixed model, extended with Week 44 and Week 48.*
- *Changes from DB-WD baseline (Week 36) to Week 40 in daytime and nighttime mean SBP and DBP measured by ABPM will be analyzed in the mFAS using the same ANCOVA as described for 24 h mean.*
- *Ratios to baseline (and DB-WD baseline [Week 36] as applicable) for all assessed time points of DB+SB and DB-WD parts in UACR will be log transformed and analyzed using a mixed model with a factor for treatment group, visit, treatment by visit interaction, covariates for baseline (DB-WD baseline [Week 36]) log UACR and visit by baseline (DB-WD baseline [Week 36]) interaction and an unstructured covariance matrix. This will be done separately for the DB+SB part on the FAS and for the DB-WD part on the mFAS.*
- *The number (%) of subjects who discontinued study treatment due to lack of efficacy will be tabulated by study part (DB, SB aprocitentan and DB-WD) and treatment group (within study part) in the FAS (2×) and mFAS, respectively. If there are at least 12 subjects discontinued due to lack of efficacy, time from Randomization to treatment discontinuation due to lack of efficacy in the DB or SB aprocitentan part will be summarized by treatment group using Kaplan-Meier plots in the FAS. For subjects who did not discontinue treatment or discontinued treatment for reasons other than lack of efficacy, time to discontinuation will be censored at the last dose of DB or SB treatment (whichever comes last). Additionally, a ‘two-step’ Cox model with a factor for treatment will be fitted [see Section 8.2 for details]. Time from Re-randomization to treatment discontinuation due to lack of efficacy in the DB-WD part will be summarized similarly in the mSAF, except that the Cox model is the conventional one. For subjects who did not discontinue treatment or discontinued treatment for reasons other than lack of efficacy in the DB-WD part, time to discontinuation will be censored at the last DB-WD treatment + 30 days (or EOS date, whichever comes first).*
- *The number (%) of subjects who initiated antihypertensive rescue medication will be summarized by study part (SB and DB-WD; rescue medication is not allowed in the DB part) and treatment group (within study part).*
- *Home SBP/DBP collected due to the COVID-19 pandemic will be summarized by visit in DB, SB and DB-WD parts using descriptive statistics.*
- *The number (%) of subjects with SBP/DBP Control will be tabulated for the DB+SB and DB-WD parts at each visit by treatment group in the FAS and mFAS, respectively. Subjects with a missing value at a given visit will be excluded from the analysis at that visit. The Cochran-Mantel-Haenszel (CMH) test will be used to test for a difference in the Control proportions at Week 4 between treatment groups in DB part on the FAS and at Week 40 between treatment groups in DB-WD part (stratified by randomized*

treatment in the DB part) on the mFAS. The treatment effect will be expressed in terms of the aprocitentan to placebo OR and corresponding 95% CI. An OR > 1 will indicate a benefit of aprocitentan as compared to placebo.

- *The number (%) of subjects with SBP/DBP Response* will be tabulated for the DB+SB and DB-WD parts at each visit by treatment group in the FAS and mFAS, respectively. Similar analyses as for control will be done at Week 4 and Week 40.

The analyses of the other endpoints are summarized in [Table 4](#).

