**Figure 1 Study design**

EOT = End-of-Treatment; FU = follow-up; V = visit.

The randomized treatment period lasts for 48 weeks [until EOT, as displayed in Figure 1]. The purpose of this period is to evaluate the primary and secondary objectives of the study. This period consists of three sequential parts:

- In the first DB part of 4 weeks, subjects will be randomized to aprocitentan 25 mg, aprocitentan 12.5 mg or placebo in a 1:1:1 ratio.
- In the second SB part of 32 weeks, all subjects will receive aprocitentan 25 mg.
- In the third DB-WD part of 12 weeks, subjects will be re-randomized at Week 36 to aprocitentan 25 mg or placebo in a 1:1 ratio.

The EOT visit will take place at Week 48 (i.e., end of DB-WD part) or earlier in the event of premature discontinuation of study treatment.

Approximately 4000 subjects were expected to be screened in order to enroll approximately 1500 subjects with a diagnosis of RHT into the SB placebo RI period. At least 600 subjects were to be randomized and at least 380 subjects were expected to be re-randomized in the DB-WD part. At least 300 subjects were expected to complete the study (including the 30-day safety FU period). The study was to be conducted at approximately 100 sites in approximately 20 countries.

The sponsor planned to look at the drop-out rate (between Randomization and Re-randomization) nine months after the randomization of the 200th subject.

If the observed drop-out rate was such that the expected number of subjects to be re-randomized in the DB-WD part was less than 380, the number of subjects randomized could have been increased to maintain at least 85% power for the DB-WD part (which is

achieved when 324 subjects are re-randomized). It appeared that the drop-out rate was lower than expected, so no sample size increase was needed to compensate for drop-out.

Ultimately, 730 subjects were randomized. The overrunning was caused by the addition of sites and countries in 2020 meant to compensate for the lower recruitment due to the Covid-19 pandemic. In order to give these new sites a reasonable chance to contribute to the study, the timelines were prolonged, which, combined with a surge in screening when the EOS was announced, lead to an over-recruitment. The study was finally conducted at 193 sites in 22 countries.

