### 5.1.3 Study treatment completion/discontinuation

A subject is considered to have prematurely discontinued treatment in the RI period if on the **Study Treatment Log** the 'Study period' is 'Single-Blind Run-in' and 'Reason for treatment stop' is 'Discontinued'.

A subject is considered to have prematurely discontinued study treatment in the DB (SB aprocitentan, DB-WD, respectively) part if on the **Study Treatment Log** the 'Reason for treatment stop' is 'Discontinued' for the corresponding 'Study period'.

Reasons for premature discontinuation are collected on the same form and include: AE, lack of efficacy, withdrawal by subject, lost to FU, death, pregnancy, and other. If the

reason for premature study treatment discontinuation was related to the COVID-19 pandemic, this was collected.

The numbers of subjects treated in the DB, SB aprocitentan and DB-WD parts will be tabulated by treatment group in the SAF, rSAF and mSAF, respectively.

The number (%) of subjects with and the reasons for premature treatment discontinuation in the RI period will be summarized based on the RIS.

The number (%) of subjects with and the reasons for premature treatment discontinuation in the randomized treatment period will be summarized by study part and treatment group (within study part) in the SAF, rSAF or mSAF, where appropriate. Reasons for premature study treatment discontinuation related to COVID-19 pandemic will also be summarized.

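### SAP 6.5.2 censors stops for other reasons in the Kaplan-Meier plot of lack-of-efficacy discontinuation, so the curve overstates the proportion who stop for that reason and disagrees with the table beside it

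*SAP*

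**What the plan says.** SAP Section 6.5.2 gives three summaries of discontinuation due to lack of efficacy.

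- **A table.** "The number (%) of subjects who discontinued study treatment due to lack of efficacy will be tabulated by study part" and treatment group, with the FAS as denominator for both the DB and SB parts and the mFAS for the DB-WD part.
- **A Kaplan-Meier plot for DB+SB, under a condition.** It is drawn "If there are at least 12 subjects discontinued due to lack of efficacy". For subjects who stopped for another reason, the rule is that they "discontinued treatment for reasons other than lack of efficacy, time to discontinuation will be censored at the last dose of DB or SB treatment".
- **A two-step Cox model** on the same times.

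For DB-WD the plan is similar, with a conventional Cox model, but subjects without the event are censored 30 days after the last DB-WD dose, or at end of study if sooner. The text names the mSAF for this analysis; Table 4 names the mFAS.

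Section 5.1.3 lists the reasons for permanent discontinuation on the treatment log as alternatives: "AE, lack of efficacy, withdrawal by subject, lost to FU, death, pregnancy, and other". Interruptions are recorded separately (Section 5.5.2). The SAP names no competing-risk estimator.

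On drop-out, Section 2.1 says: "At least 600 subjects were to be randomized and at least 380 subjects were expected to be re-randomized in the DB-WD part". It adds: "It appeared that the drop-out rate was lower than expected, so no sample size increase was needed to compensate for drop-out".

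**The concern.** Treatment can be stopped permanently only once. A subject who stops for an adverse event, withdraws, is lost to follow-up or dies has left the population that can still stop for lack of efficacy. Kaplan-Meier treats that subject as if the event could still happen later, at the same rate as in those still on treatment. So 1-KM describes a setting in which nobody stops for any other reason. It does not give the share of randomized subjects who stop for lack of efficacy.

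The practical consequence is a report with two figures for one endpoint. If every subject is followed to Week 36 or to discontinuation, the FAS percentages summed over DB and SB are essentially the correct cumulative incidence. The curve next to them will end higher, and nothing in the SAP explains the gap.

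The DB-WD rule adds a second problem. Censoring 30 days after the last dose keeps subjects in the risk set when they are off treatment and cannot have the event. That curve is neither a Kaplan-Meier estimate with censoring at last dose nor a cumulative incidence.

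**Working it through.** **Inputs from the documents.** 600 randomized and 380 re-randomized (planned); 4 + 32 = 36 weeks of follow-up in DB+SB; a 12-event threshold for the plot. The SAP states neither a lack-of-efficacy incidence nor a drop-out percentage, so there is no plan figure to reproduce.

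**Assumptions.** Subjects not re-randomized are taken as off treatment by Week 36. The share f of drop-outs due to lack of efficacy is not given, so a range is used. Cause-specific hazards are proportional unless stated.

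**Formulas.**
- Drop-out d = 1 - 380/600 = 0.367, which is 220 of 600.
- Total cumulative hazard H = -ln(1 - d) = 0.457.
- True cumulative incidence = f × d.
- 1-KM with other reasons censored = 1 - exp(-f × H).

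**Result at 36.7% drop-out.**

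| f | True incidence | 1-KM | Relative excess |
|---|---|---|---|
| 5.5% (12 of 220) | 2.00% | 2.46% | +23% |
| 10% | 3.67% | 4.46% | +22% |
| 20% | 7.33% | 8.73% | +19% |
| 25% | 9.17% | 10.79% | +18% |
| 50% | 18.3% | 20.4% | +11% |

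For f from 5.5% to 25% the absolute excess runs from 2.46 - 2.00 = 0.46 to 10.79 - 9.17 = 1.62 points.

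**Lower drop-out (f = 5-25%).** +14-18% at 30% drop-out, +9-11% at 20%, +4-5% at 10%.

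**Other timing (d = 36.7%, f = 5.5-25%).**

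| Pattern | Relative excess |
|---|---|
| Lack-of-efficacy stops all in Weeks 0-4 | about +2% |
| Lack-of-efficacy stops all in Weeks 0-12 | +5-6% |
| Lack-of-efficacy stops all in Weeks 18-36 | +27-36% |
| Other stops all in Weeks 0-12 | +32-43% |

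**Against sampling error.** With 730/3 = 243 subjects per arm and SE = sqrt(p(1 - p)/243), true incidences of 3%, 5% and 8% at 36.7% drop-out are drawn as 3.7%, 6.0% and 9.5%. The shifts are 0.61, 0.74 and 0.85 SE of a single arm. This pairs the planned drop-out with the actual sample size.

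**Does the bias create a difference between arms?** Take two arms with the same cumulative lack-of-efficacy hazard, 0.06, and other-cause hazards of 0.40 and 0.20 (illustrative).
- 1-KM = 1 - exp(-0.06) = 5.82% in both arms.
- Cumulative incidence = (0.06/0.46) × (1 - exp(-0.46)) = 4.81% in the first arm.
- Cumulative incidence = (0.06/0.26) × (1 - exp(-0.26)) = 5.28% in the second.

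The gap between the two estimators is wider where other stops are more common, but that is because the cumulative incidence is lower there. The Kaplan-Meier curve itself does not move.

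**The case against.** The best defence is that the plan is coherent on the hazard scale. Censoring other stops at last dose is what a cause-specific Cox model requires, and Kaplan-Meier is its companion plot. The table already supplies the incidence, and the SAP never says that 1-KM will be reported as one. Much of this stands. The DB+SB Cox model is valid as a cause-specific analysis, and a careful reader can take the proportion from the table. It does not rescue the plot, which will be read as the proportion who stop for lack of efficacy and is not labelled otherwise.

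A second objection is that the size rests on inputs the SAP does not give. That is also right. A reader might infer that the actual curves will be a fifth too high. The documents do not support this, because the 36.7% is a planning figure derived from two minimum numbers and Section 2.1 says drop-out was lower than expected.

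A reader might also infer that Kaplan-Meier would make a tolerability difference between arms look like a difference in lack of efficacy. It would not. With independent causes 1-KM contains no other-cause hazard, as the two-arm example shows. It is the cumulative incidence curve that responds to other stops: the arm with more of them shows fewer lack-of-efficacy stops. This is a real, if small, drawback of the remedy.

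Finally, the 36.7% does not carry over to DB-WD, which has its own drop-out and its own censoring rule. No size is claimed for that part.

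**Conclusion.** The point holds, at low severity. Discontinuation for other reasons is a competing event, and censoring it makes the plotted 1-KM exceed the proportion who stop for lack of efficacy and disagree with the table in the same bullet. The direction does not depend on the assumptions; the size does. The 18-23% relative excess needs the planning drop-out of 36.7%, proportional hazards and lack of efficacy as about 5-25% of drop-outs. With the lower drop-out that the SAP reports without a figure, the excess would be smaller under the same assumptions, and event timing could move it either way.

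The consequences are confined to an exploratory plot that appears only if the 12-subject threshold is met. The endpoint lies outside the three-hypothesis testing strategy of Section 6.1, so no confirmatory result is affected.

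**What to change.** In SAP Section 6.5.2:

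1. Replace the Kaplan-Meier plots of lack-of-efficacy discontinuation, in DB+SB and in DB-WD, by Aalen-Johansen cumulative incidence curves by treatment group, with discontinuation for any other reason as the competing event.
2. Keep the Cox models and label their hazard ratios cause-specific.
3. For DB-WD, count an other-reason stop as a competing event at the last dose, in place of censoring 30 days later. Apply last-dose timing to the Cox model as well, so that nobody is counted at risk after treatment has ended.
4. Reconcile the DB-WD analysis set: mSAF in the text, mFAS in Table 4.
5. Add a sentence that the curves also depend on the rate of other-reason stops and are to be read together with the cause-specific hazard ratios.

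The cost is a few SAP sentences and a standard procedure option. The reasons for stopping are already collected, and neither alpha nor the main analyses change.
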